## **Introduction**

Hepatocellular carcinoma (HCC) is one of the leading causes of death in patients with cirrhosis (1). It is the sixth most common neoplasm in the world, with more than a half million newly diagnosed cases annually (2,3). The etiology is unknown but it is reported mainly in patients with cirrhosis and patients with chronic hepatitis B infection (HBV) (2). Surgical resection and liver transplant are potential curative treatments for patients who meet Milan criteria (Appendix 1) or have  $\leq$  2cm solitary lesion (3,4).

CT scan or Magnetic Resonance Imaging (MRI) of the abdomen with/without alpha fetoprotein (AFP) is an important tool for early detection. HCC is diagnosed in patients with cirrhosis by one imaging technique showing a nodule larger than 2 cm with contrast uptake in the arterial phase and washout in venous or late phase, or two imaging techniques showing this radiological behavior for nodules of 1-2 cm in diameter (3). Cytohistological confirmation is required for patients who do not fulfill these criteria (3,4).

Multiple treatments are available. The best appropriate treatment is determined according to hepatic function reserve as represented by Child-Pugh-Turcotte class (Appendix 2), and tumor size and number. Patients who are surgically fit with Child class A and solitary lesion  $\leq$  2 cm are best treated by tumor resection. Liver transplantation is the best treatment for patients with unresectable lesion(s) that meet the Milan criteria (5) (Appendix 1).

Patients with tumor burden that exceeds Milan criteria are considered to receive one of the following locoregional treatments: transarterial chemoembolization (TACE), radiofrequency ablation (RFA), percutaneous ethanol injection and proton beam radiation (6). The goals of these treatments are to control tumor growth, to downstage tumor size to meet Milan criteria, and to improve survival. Patients who exceed the Milan criteria benefit from downstaging, so they can be qualified for liver transplant. Patients who meet Milan criteria benefit from tumor control to bridge them to liver transplantation (6,7). TACE is considered the most common locoregional treatment that is used to treat HCC. Proton beam radiotherapy has been used in treating HCC in a few centers across the globe. Phase I and II trials showed a satisfactory safety and efficacy results. Loma Linda University Medical Center is one of these pioneering centers that use proton beam as a treatment for HCC (ref). This is the first randomized trial in the medical field that will compare head-to-head the efficacy of TACE versus proton beam in treating HCC patients.

## **Transarterial Chemoembolization (TACE)**

Multiple studies have shown contradictory results regarding the efficacy of TACE in improving survival compared to other treatments. The majority of these studies are retrospective studies or used a small sample of patients. These contradictory results have been attributed to the difference in endpoints of these studies and the multiple variables such as tumor size and liver function that usually impact and confound the outcome.

In one large study involving several institutions in Italy, chemoembolization did not improve survival compared to supportive care only. Patients who did not undergo TACE lived as long as patients who received TACE, even though the tumors were more likely to shrink in size in patients who were treated (8). Llovet et al. used TACE as a palliative treatment in a prospective, randomized controlled trial published in 2002 on 112 patients with intermediate stage HCC not felt to be candidates for other therapies. The patients randomized to TACE versus supportive care only. A significant increase in survival for the chemoembolization group was observed when compared with control (82% and 63%, 1-and 2-year survival, respectively, compared with 63% and 27%) (9). A study in Japan has shown that TACE can downstage liver cancer (10). Downstaging created the option for transplant in some of these patients. Otherwise, these patients had tumors that were not operable (eligible for operation) or not qualified for liver transplantation because of the initial large size of their tumors (10). More importantly, this study showed an improvement in survival in patients whose tumors became considerably smaller. In the U.S., trials are underway to see whether doing TACE before liver transplantation increases patient survival as compared to liver transplantation without TACE. Risk and common side effects of TACE include: bleeding, infection, worsening liver function, perforation of the common bile duct, veins or arteries, abdominal pain, nausea, vomiting, and fever.

It is reasonable to conclude that TACE is a procedure with acceptable side effects and a controversial small advantage in improving survival, especially in patients with small tumor and for patients waiting for liver transplantation. TACE can be used only in patients with relatively preserved liver function. The reason for this is that these procedures, as mentioned previously, can lead to liver failure in individuals with poor liver function.

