## ***Methods***

Patients meeting the inclusion and exclusion criteria will be randomized (1:1) by an individual who is not a study investigator using the random number method. Subjects will be registered and randomized by contacting [name] ([name], [[contact]](mailto:[contact])). Subjects will be randomly assigned to one of two groups:

Group 1: patients will receive one or more sessions of TACE (Appendix 3).

Group 2: patients will receive 15 consecutive sessions of proton beam radiation (Appendix 4).

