## ***Primary Endpoint***

The primary end point of the study is to measure ***overall survival*** defined as the time from randomization until death. In order to control for non-cancer death related factors that may compound the survival rate, a competing risk analysis rather than Kaplan-Meier will be used to compare the survival between the two groups.

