## **Data and Statistics**

Data will be evaluated according to intent to treat analysis. One- and two-year survival will be compared between two groups using competing risk analysis. This analysis will provide an estimate of HCC-related death in the presence of alternate yet plausible outcomes such as death from liver failure or liver transplantation. It is also a better technique in illustrating differential rates of competing outcomes in patients waiting for liver transplantation. This analysis will limit the effects of confounding factors such as death from liver disease. Secondary end points will be compared using Student's *t*-test for quantitative data and chi-squared ( $\chi^2$ ) test or Fisher's exact test for qualitative data. Demographics and standard of care laboratory data between groups will be compared. Logistic regression will be used to determine independent factors affecting survival.

The study is designed and powered to show at least 15% difference in mortality between two groups. Group size is calculated by assuming that patients in the TACE group will have at least 15% improvement in 2-year survival compared to the proton beam group. With 110 patients in each group the study has 80% power to detect a 15% difference in the mortality between two groups. We are not expecting any significant drop out because both treatments are considered crucial for patients' survival; and also based on our experience in treating these patients for many years at LLUMC. The level of significance is 0.05 (2-sided) for all statistical tests. The Statistical Package for the Social Sciences (SPSS 16.0 for window; SPSS, Inc., Chicago, Illinois) was used for all statistical analyses.

We will conduct an interim analysis after randomizing 40 patients in each group. This analysis will determine if there is any early significant difference in survival between two groups. The interim report will be submitted to the Institutional Review Board.

Data will be collected anonymously and subjects will be identified using a numerical code. The code will be stored at the PI and Co-PI office. The study database will be maintained and stored in the department of radiation medicine. Only PI, CO-PI and research coordinators will have access to the data.

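### The primary survival comparison names no baseline covariate or stratum, although the protocol treats tumour size and liver function as drivers of outcome; prespecified adjustment would recover precision at almost no cost

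*Combined protocol and SAP*

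**What the plan says.** - **Prognosis.** The section on Transarterial Chemoembolization (TACE) explains the conflicting literature partly by "multiple variables such as tumor size and liver function that usually impact and confound the outcome". The Introduction says that choice of treatment depends on Child-Pugh class and on tumour size and number.
- **Spread at entry.** The Exclusion Criteria remove Child C and MELD above 25, so Child A and B both enter. The Inclusion Criteria allow tumours up to the San Francisco limits in Appendix 1. The Downstaging endpoint is written for patients who are beyond Milan but within those limits.
- **Allocation.** Methods says that patients are "randomized (1:1) by an individual who is not a study investigator using the random number method". No strata, blocks or minimization are described.
- **Primary comparison.** Overall survival is "defined as the time from randomization until death". Data and Statistics adds: "One- and two-year survival will be compared between two groups using competing risk analysis". Neither section names a baseline covariate.
- **Nearby text.** Of the competing-risk method, the plan says "This analysis will limit the effects of confounding factors such as death from liver disease". It also says "Demographics and standard of care laboratory data between groups will be compared" and "Logistic regression will be used to determine independent factors affecting survival".

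**The concern.** The plan identifies two baseline features as prognostic, lets both vary among eligible patients, and needs both recorded to decide eligibility and downstaging. The treatment comparison then uses neither.

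None of the nearby text fills the gap. Treating liver death or transplant as a competing event sorts outcomes by type; it does not account for liver function or tumour burden at entry. The logistic regression lists no covariates, is not tied to the treatment effect, and takes no account of event time or censoring. Comparing baseline data, with no rule for what follows, leaves covariates to be chosen after the data are seen.

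At stake are some power and protection against a chance imbalance in a strong prognostic factor. That protection matters most at the small interim analysis.

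**Working it through.** **1. The plan's own figure.** Data and Statistics claims 80% power with 110 per group for a 15% difference in mortality, two-sided 0.05, and gives no base rate. For an absolute difference of 0.15, with p the mean of p1 and p2:

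n = [1.96·√(2p(1−p)) + 0.842·√(p1(1−p1) + p2(1−p2))]² / 0.15²

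- 88% v 73%: n = 109 per group; power at 110 is 80.6%. This reproduces the claim, as do 87% v 72%, 27% v 12% and 28% v 13%.
- 63% v 48%: n = 172 per group; power at 110 is 61%. Here 63% is the only 2-year TACE survival figure in the documents (TACE section).

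The missing base rate is a separate matter. It matters here because power may not be plentiful.

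**2. Gain from adjustment.** Inputs from the plan: 110 per arm, two-sided 0.05, a 15-point difference at 2 years. Assumed, because the documents are silent: two independent binary factors (standing for Child B and beyond Milan), 40% prevalence each, and equal prognostic hazard ratios (HR). Method: exponential survival, follow-up cut at 2 years, Cox model for all-cause death with arm only versus arm plus both factors, 2,000 trials per cell. Simulation error is about 1 point.

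| 2-year survival | HR 1.5 each | HR 2 each | HR 3 each |
|---|---|---|---|
| 63% v 48% | 63% → 64% | 62% → 68% | 63% → 77% |
| 73% v 58% | 64% → 65% | 65% → 70% | 66% → 78% |
| 63% v 78% | 69% → 70% | 67% → 71% | 69% → 78% |
| 88% v 73% | 80% → 81% | 80% → 82% | 80% → 85% |

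A second design takes a true treatment hazard ratio of 1.5. It was run with censoring uniform over 24 to 60 months (about 133 deaths), and with the same hazards cut at 24 months (about 95 to 98 deaths):

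| Prognostic HRs | 24–60 months | Cut at 24 months |
|---|---|---|
| 1.5 and 1.5 | 61% → 64% | 47% → 48% |
| 2.0 and 1.5 | 57% → 64% | 47% → 50% |
| 2.5 and 1.5 | 57% → 64% | 44% → 50% |
| 3.0 and 2.0 | 49% → 65% | 41% → 50% |

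Across both tables the gain is about 1 to 3 points for weak factors, 2 to 7 near a hazard ratio of 2, and 5 to 16 near 3. In the first table it is smallest where survival is high; in the second it shrinks when follow-up is cut to 24 months.

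**3. Type I error.** With no treatment effect, rejection rates unadjusted and adjusted are 5.1% and 5.4% (HR 2), and 4.9% and 5.3% (HR 3). Both analyses are valid.

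**4. Chance imbalance under simple randomization, one factor at 40%.** SD of the arm difference = √(2 × 0.4 × 0.6 / n).

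- n = 110: SD = 0.066; 0.10/0.066 = 1.51; two-sided probability 13%.
- n = 40 (interim): SD = 0.110; 0.10/0.110 = 0.91; two-sided probability 36%.

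**5. Consequence of imbalance, no true effect, 110 per arm, 63% survival at 2 years.**

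- One factor off by 10 points: the average unadjusted hazard ratio is 1.04, 1.06 or 1.10 for prognostic HRs of 1.5, 2 or 3. The false-positive rate stays at 4% to 5%.
- Both factors off by 10 points in the same direction: 1.08, 1.14 or 1.22, with false-positive rates of 6%, 9% and 13%. Adjusted, the rate stays at 4% to 6%.
- If the factors are independent, a same-direction double imbalance of at least 10 points has probability about 2 × 0.065² = 0.8% at 110 per arm, and about 2 × 0.18² = 6.5% at 40 per arm.

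**The case against.** **Randomization already deals with confounding.** The TACE background explains disagreement among earlier studies that were mostly retrospective or small. A reader might infer that the unadjusted comparison here is confounded or invalid. The documents do not support that: allocation is randomized, and type I error is about 5% either way. What stands is that the sentence is the protocol's own evidence that these factors affect outcome.

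**Attenuation is not bias.** A reader might say that omitting covariates biases the hazard ratio toward 1. In the second design the unadjusted average does fall below the true 1.5 (1.41 with prognostic HRs of 3.0 and 2.0). But the unadjusted and adjusted hazard ratios are different quantities, and the plan speaks of one- and two-year survival rather than a hazard ratio. The argument for adjustment is power, not correction of a wrong estimate.

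**The size is assumed.** This stands in full. No prevalence or prognostic strength is in the documents, and eligibility already narrows the range (Child C, MELD above 25, AFP above 500, metastasis and macrovascular invasion are all excluded). The simulations also use all-cause Cox models and leave out transplant, because the plan does not name its competing-risk test or model.

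**Silence is not proof.** Methods says only "using the random number method". That allocation is simple and unstratified is a reading of what is not described. Likewise, arm could be a term in the unlisted logistic model. Even so, that model would not be the primary comparison.

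**A single imbalance does little.** This also stands at full size: one factor off by 10 points barely changes the false-positive rate.

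**Conclusion.** The concern holds as one of efficiency and protection against imbalance, not of validity. No baseline covariate or stratum is named for the primary comparison, although the protocol calls the factors prognostic and already needs them at entry.

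On the assumptions above, adjustment is worth about 1 to 3 points of power for weak factors, 2 to 7 near a hazard ratio of 2, and 5 to 16 near 3. A reader might take the upper end as the expected loss; nothing in the documents says that these factors are that strong. The 13% and 36% imbalance probabilities assume simple randomization and 40% prevalence. The change is worth making because it is nearly free and the plan may have little power to spare.

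**What to change.** In Data and Statistics, state before any outcome is examined that the primary treatment comparison comes from a time-to-event regression with arm, Child class (A/B) and Milan status (within/beyond). Apply it to whichever survival endpoint and competing-event handling the plan settles on; this point does not require replacing the competing-risk method. Keep the unadjusted comparison as supportive.

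AFP may be added if its functional form is stated. MELD is not needed beside Child class, because both use bilirubin and INR (Appendices 2 and 5).

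**Cost:** a short amendment to the analysis text. Eligibility and the downstaging endpoint already require the covariates, so no visit, test or patient is added. The adjusted effect is conditional on the covariates and differs slightly in meaning from the unadjusted one, so the report should say which is primary. Stratified allocation is optional; the fix does not depend on it.

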## **Proton Beam Radiotherapy**

Proton beam radiotherapy has physical properties that target the actual tumor mass and spare large portions of nearby normal tissues. Phase I and II trials demonstrated the safety of this treatment modality in decompensated patients with cirrhosis with HCC. Few trials in Southeast Asia and the United States demonstrated that proton beam could be an effective treatment that may improve survival and control tumor progression. Tokuyue et al. treated 79 patients who had HCC with proton beam radiotherapy (12). A median total dose of 72 Cobalt gray equivalents in 16 fractions was delivered. At 5 years, local tumor control and survival rates were 89% and 27% respectively. Kawashima et al. used the same fractionation scheme in 30 patients with HCC with an indocyanine green retention rate at 15 minutes. Complete disappearance of tumors occurred in 24 patients (80%). The 2-year local regression-free rate in that study was 96%, and the 1-year and 3-year survival rates were 77% and 62% respectively (13). Eight patients developed hepatic insufficiency, which presented as ascites, elevated transaminase levels, and/or asterixis from 1 to 4 months after therapy (13). Bush et al., in a phase II trial where 34 patients with HCC completed 15 sessions of total 63 cobalt Gray equivalents, 75% local tumor control rate and overall survival rate of 55%. Six patients underwent liver transplantation 6 to 18 months after proton therapy. In 2 patients, there was no evidence of tumor pathology, demonstrating that proton therapy can eradicate HCC (14). A complete pathologic response was also observed by Merle et al (15). Risks involved in proton treatment include internal bleeding, radiation hepatitis (elevation in liver enzymes), worsening liver function (elevation in

bilirubin and INR) and perforation of the surrounding solid organ such as small bowel and stomach.

Proton beam radiotherapy has been associated with some of the best outcomes in HCC patients; however, further studies are needed to compare proton to other treatments.

In this randomized trial we wish to compare head-to-head the efficacy of proton beam radiotherapy versus TACE in treating patients with unresectable HCC.

## **Aim of The Study**

This study aims to compare the efficacy of TACE versus proton beam radiotherapy in treating cirrhotic patients with HCC who meet San Francisco criteria.

## **Study Design**

This is a randomized controlled trial targeting HCC patients at Loma Linda University Medical Center (LLUMC) and the Inland Empire area. The diagnosis of HCC will be determined according to one abdominal imaging (CT scan or MRI) performed within 3 months of randomization showing characteristics of HCC. These characteristics include including one or more nodules (2 cm) hypervascular or with contrast uptake in the arterial phase and washout in venous or late phase or two imaging techniques showing this radiological behavior for nodules of 1-2 cm in diameter. An independent radiologist at LLUMC will verify the diagnosis of HCC. Patients with cirrhosis with liver tumor that does not fulfill these criteria will need a cytopathological confirmation of HCC.

The diagnosis of cirrhosis will be determined clinically and radiologically in patients with chronic liver disease by the presence of thrombocytopenia with or without coagulopathy, and splenomegaly with irregular liver surface with or without liver biopsy showing bridging fibrosis and regenerative nodules.

## **Patients**

Patients with cirrhosis and HCC who are not candidates for surgical resection will be targeted for enrollment. Patients will be recruited from the liver clinics at the Transplantation Institute and Faculty Medical Office. Patients from the Inland Empire area will be invited to participate as well. Community physicians will be informed of the study via mail and will be encouraged to refer their patients for participation (see attached letter No 1). Patients who are qualified to receive both TACE and proton treatments will be included. CT scan of the chest and bone scan within 6 months is required to exclude the presence of metastasis. Macrovascular invasion will be excluded using MRI or CT scan of the abdomen that will be performed within 3 months of enrollment.

Interventional radiologists and a radiation oncologist at LLUMC will evaluate the patient's case independently prior to randomization if the candidate is qualified to receive both treatments. Contraindications to receive TACE are: Child class C, hypovascular lesion and active sepsis. Contraindications to proton are: tense ascites requiring frequent paracentesis or proximity to a hollow organ such as the stomach or small intestine.

## ***Inclusion Criteria***

1. Patients are candidates to receive both proton beam and TACE
2. Patients with no evidence of metastasis or macrovascular invasion
3. Patients with tumor burden that meets San Francisco criteria (Appendix 1)

## ***Exclusion Criteria***

1. Patients who are candidates for surgical resection
2. Patients with lesion < 2 cm
3. Patients who have contraindication to receive either TACE or proton
4. Patients with serum alpha fetoprotein > 500
5. Patients with metastasis or macrovascular invasion
6. Patients treated previously for HCC by any locoregional treatment
7. Patients with prior liver transplant
8. Patients with Child class C
9. Patients with MELD score of > 25 (Appendix 5)
10. Patients with other comorbid diseases that may impact survival
11. Patients with ongoing alcohol intake
12. Patients with active sepsis
13. Patients with gastrointestinal bleeding within a week
14. Patients unwilling to sign informed consent form
15. Patients with history of noncompliance

## ***Methods***

Patients meeting the inclusion and exclusion criteria will be randomized (1:1) by an individual who is not a study investigator using the random number method. Subjects will be registered and randomized by contacting [name] ([name], [[contact]](mailto:[contact])). Subjects will be randomly assigned to one of two groups:

Group 1: patients will receive one or more sessions of TACE (Appendix 3).

Group 2: patients will receive 15 consecutive sessions of proton beam radiation (Appendix 4).

## ***Primary Endpoint***

The primary end point of the study is to measure ***overall survival*** defined as the time from randomization until death. In order to control for non-cancer death related factors that may compound the survival rate, a competing risk analysis rather than Kaplan-Meier will be used to compare the survival between the two groups.

